8.4.13 Hypoglycaemic episodes

At randomisation, all subjects must be instructed in symptom recognition and handling of hypoglycaemia.

Plasma glucose should always be measured and recorded when a hypoglycaemic episode is suspected.

All plasma glucose values:

- \leq 3.9 mmol/L (70 mg/dL) or
- $>$ 3.9 mmol/L (70 mg/dL) occurring in conjunction with hypoglycaemic symptoms

should be reported in the diary according to the instructions below throughout the trial from randomisation to V25. See Section [8.6.3.2](#).

Upon onset of a hypoglycaemic episode the subject is recommended to measure plasma glucose every 15 minutes until the SMPG value is $>$ 3.9 mmol/L (70 mg/dL) and/or symptoms have been resolved in accordance to current guidelines⁴⁸.

A SMPG value \leq 3.9 mmol/L (70 mg/dL) or hypoglycaemic symptoms must trigger a hypoglycaemic episode form to be completed by the subject. Repeated SMPG measurements and/or symptoms, occurring within a period of 60 min after onset on a hypoglycaemic episode, will by default be considered as one hypoglycaemic episode until a succeeding SMPG value is $>$ 3.9 mmol/L (70 mg/dL) and/or symptoms have been resolved and should be reported on one hypoglycaemic episode form. SMPG measurements \leq 3.9 mmol/L (70 mg/dL) or hypoglycaemic symptoms after the 60 min period shall trigger the reporting of a new hypoglycaemia episode and prompt the subject to fill out a new hypoglycaemic episode form until a succeeding measurement is $>$ 3.9 mmol/L (70 mg/dL) and/or symptoms have been resolved.

In case of several low SMPG values within the 60 minutes interval, the lowest value is the one that will be reported as the SMPG value for the hypoglycaemic episode but the start time of the episode will remain as the time for the first SMPG value and/or symptom.

The record should include the following information:

- Start date and time of the hypoglycaemic episode.
- The plasma glucose level before treating the episode (if available) and any follow up measurements.
The lowest value measured during the hypoglycaemic episode will be reported as the plasma glucose value for the episode. The remaining values will be kept as source data in the diary.
- Whether the episode was symptomatic (Yes/No).
A hypoglycaemic episode starting without symptoms should be updated to symptomatic if the subject experience symptoms later during the episode.

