12.1 Definitions

12.1.1 Adverse event

An adverse event (AE) is any untoward medical occurrence in a subject administered a medicinal product, and which does not necessarily have a causal relationship with this treatment.

An AE can therefore be any unfavourable and unintended sign (including an abnormal laboratory finding), symptom or disease temporally associated with the use of a product, whether or not considered related to the product.

An AE includes:

- A clinically significant worsening of a concomitant illness.
- A clinical laboratory adverse event (CLAE): a clinical laboratory abnormality which is clinically significant, i.e. an abnormality that suggests a disease and/or organ toxicity and is of a severity that requires active management. Active management includes active treatment or further investigations, for example change of medicine dose or more frequent follow-up due to the abnormality.

The following should **not** be reported as AEs:

- Pre-existing conditions, including those found as a result of screening or other trial procedures performed before exposure to trial product (pre-existing conditions should be reported as medical history or concomitant illness).
- Pre-planned procedures unless the condition for which the procedure was planned has worsened from the first trial-related activity after the subject has signed the informed consent.
- Non-serious hypoglycaemia is an AE, but is reported on a hypoglycaemic episode form instead of on an AE form; see Section [8.4.13](#).

The following three definitions are used when assessing an AE:

- **Severity**
 - **Mild** – no or transient symptoms, no interference with the subject's daily activities.
 - **Moderate** – marked symptoms, moderate interference with the subject's daily activities.
 - **Severe** – considerable interference with the subject's daily activities; unacceptable.
- **Causality**

Relationship between an AE and the relevant trial products:

 - **Probable** - Good reason and sufficient documentation to assume a causal relationship.
 - **Possible** - A causal relationship is conceivable and cannot be dismissed.
 - **Unlikely** - The event is most likely related to aetiology other than the trial product.

- **Final outcome**

- **Recovered/resolved** - The subject has fully recovered, or by medical or surgical treatment the condition has returned to the level observed at the first trial-related activity after the subject signed the informed consent.

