17.1 Sample size calculation

This is a superiority trial comparing liraglutide to placebo. Superiority will be claimed if the p-value is less than 5% and the treatment favours liraglutide.

It is anticipated that the effect of liraglutide in adolescents with obesity will be similar to the effect observed in adults. The anticipated treatment difference for BMI SDS³³ is based on the results from trial NN8022 1839 in adults with overweight and obesity. For the sample size scenarios, treatment differences of -0.24, -0.26, and -0.28 were investigated.

The standard deviation (SD) is assessed based on publications by Reinehr et al. 2009¹³ Berkowitz et al. 2003⁵⁶ and trial NN8022-3967 in adolescents with obesity aged 12–17 years. For the sample size scenarios, SD of 0.25, 0.35 and 0.45 were investigated.

The effect of withdrawals on the analysis is accounted for as a reduction of the anticipated treatment difference and increase of the SD. Since a conservative imputation method is planned for the main analysis of the primary endpoint, it is assumed that withdrawn subjects respond as if treated with placebo for the entire trial. The assumed withdrawal percentage for this paediatric trial is 40% at week 56. A higher withdrawal percentage is assumed for this trial than what was seen in trial NN8022-1839 in adults, because this trial will include an adolescent trial population.

The total number of subjects is shown for the investigated scenarios in [Table 17–1](#) for 90% and 99% power.

Table 17–1 Sample size calculations for different scenarios with total number of randomised subjects

POWER	Treatment difference (completers)	SD		
		0.25	0.35	0.45
90%	-0.24	144	266	428
	-0.26	124	228	366
	-0.28	110	200	318
99%	-0.24	248	462	746
	-0.26	216	398	638
	-0.28	190	346	554

Based on the above mentioned references, it seems realistic and conservative to assume an SD of 0.35 and a treatment difference of –0.26. The minimum requirement in the Paediatric Investigation Plan is 154 randomised subjects while FDA requires a minimum of 100 subjects exposed to liraglutide. A sample size of 228 randomised subjects gives a power of 90%. Thus, the number of randomised subjects should be 228.

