17.4.1.2 Safety endpoints

Adverse events

AEs will be summarised for the safety analysis set separately for three periods:

- Run-in period: defined as events with onset date between V2 (included) and the first day of trial product administration (not included).
- In-trial period: defined as events with onset date between the first day of trial product administration and the last study visit.
- On-treatment period: defined as events with onset date between the first day of trial product administration and whatever comes first: a) 14 days after the last day on trial product , b) follow-up visit (V26 for subjects with trial product discontinued), or c) last study visit (subjects withdrawn without follow-up visit).

A treatment-emergent adverse event (TEAE) is defined as an event that occurs in the “on-treatment” period.

The AEs will be coded using the most recent version of the Medical Dictionary for Regulatory Activities (MedDRA). They will be presented in terms of the number and percentage of subjects with at least one event, the number of events and the event rate per 1000 years. AEs in the screening period (prior to randomisation) will be presented in listings.

Hypoglycaemic episodes

Hypoglycaemic episodes will be summarised descriptively by severity and treatment in terms of the number and percentage of subjects with at least one episode and the total number of episodes. Separate summaries will be made by severity (the ISPAD criterion for severe hypoglycaemia⁴⁹). In

the same way as for AEs, there will be separate summaries for the “in-trial” and “on-treatment” periods. Hypoglycaemic episodes in the screening period will be presented in listings.

Classification of Hypoglycaemia

Treatment emergent: hypoglycaemic episodes will be defined as treatment emergent if the onset of the episode occurs on or after the first day of trial product administration, and no later than 14 days after the last day on trial product.

Nocturnal hypoglycaemic episodes: are episodes occurring between 23:00 and 07:00 both inclusive.

[figure not shown]
Hypoglycaemic episodes are classified according to ISPAD’s definition of severe hypoglycaemia⁴⁹ as well as the Novo Nordisk classification of hypoglycaemia; see [Figure 17–1](#) and the ADA classification of hypoglycaemia; see [Figure 17–2](#)).

Novo Nordisk classification of hypoglycaemia in paediatrics

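### Hypoglycaemic episodes get no exposure-adjusted rate although AEs in the same section do; raw counts and percentages would mislead if on-treatment exposure differs between arms

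*Protocol*

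**What the plan says.** Protocol 17.4.1.2 sets out two neighbouring safety summaries.

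- **Adverse events**: number and percentage of subjects with an event, and "the number of events and the event rate per 1000 years".
- **Hypoglycaemia**: "Hypoglycaemic episodes will be summarised descriptively by severity and treatment in terms of the number and percentage of subjects with at least one episode", plus the total number of episodes. No rate is listed. The phrase linking this paragraph to the AE paragraph carries over only the split by period: "there will be separate summaries for the “in-trial” and “on-treatment” periods".

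An episode is treatment-emergent if it starts on or after the first day of trial product and "no later than 14 days after the last day on trial product". Under Protocol 8.4.13, low glucose values and symptomatic episodes go in the diary "throughout the trial from randomisation to V25". Protocol 12.1.1 keeps most episodes out of the AE forms: "Non-serious hypoglycaemia is an AE, but is reported on a hypoglycaemic episode form instead of on an AE form".

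SAP 2.4.1.2 lists the endpoint as a number of treatment-emergent episodes and says the safety descriptives are meant to compare liraglutide with placebo. Neither that section, SAP 2.7 (reporting) nor SAP 3.3 (changes to safety analyses) adds a hypoglycaemia rate.

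On attrition, Protocol 17.1 says: "The assumed withdrawal percentage for this paediatric trial is 40% at week 56". This is a single sample-size assumption with no split by arm.

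**The concern.** The treatment-emergent window closes 14 days after each subject's last dose, so a subject who stops early has less time in which to contribute an episode. Neither the total number of episodes nor the percentage of subjects with at least one allows for this. The AE summary does, through its rate.

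If the arms differ in how many subjects stop trial product, or in when they stop, the arm with less exposure will show fewer episodes at the same underlying hazard. Depending on which arm that is, the raw figures could understate or overstate a liraglutide effect on hypoglycaemia. A reader given only the planned hypoglycaemia table could not tell which.

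**Working it through.** **Does any part of the plan already supply the rate?**

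- Protocol 17.4.1.2 lists the hypoglycaemia measures in their own sentence, without a rate, and the cross-reference to AEs concerns periods only.
- The AE rate does not clearly cover the endpoint, because non-serious episodes are recorded on a separate form (12.1.1). Only episodes meeting SAE criteria also go on an AE form (8.4.13).
- The SAP adds nothing.

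The omission is confirmed.

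**The plan's own figure.** No number is stated for hypoglycaemia. The 40% is used only in the sample size, and that reproduces:

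- Diluted difference: 0.6 × 0.26 = 0.156.
- Liraglutide-arm SD: √(0.35² + 0.4 × 0.6 × 0.26²) = 0.3725. Placebo SD: 0.35. Root mean square: 0.3614.
- Two-sided 5%, 90% power: 226 in total by the normal approximation, 228 by the noncentral t. The plan states 228, or 114 per arm.

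So the 40% is a working assumption of the design, applied as one overall figure.

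**Illustration of size.** Inputs from the documents: 114 per arm and 56 weeks of treatment (56/52 = 1.077 years). Assumptions of this review:

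- the by-arm splits, chosen to average 40%;
- withdrawal as a proxy for stopping drug;
- stopping on average at mid-treatment;
- a constant hazard, equal in both arms;
- the 14-day tail ignored.

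Mean exposure fraction = 1 − w/2, where w is the proportion stopping. Person-years = 114 × 1.077 × (1 − w/2). At equal hazard the ratio of expected counts equals the ratio of exposure.

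| Stopping, arm A vs arm B | Person-years, A vs B | Count ratio A/B |
|---|---|---|
| 40% vs 40% | 98.2 vs 98.2 | 1.00 |
| 45% vs 35% | 95.1 vs 101.3 | 0.775/0.825 = 0.94 |
| 50% vs 30% | 92.1 vs 104.4 | 0.75/0.85 = 0.88 |

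Swapping the arms inverts the ratio (1.07 and 1.13).

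*Effect of the 14-day tail.* Stoppers gain 2/56 = 0.036 of the treatment period, so their fraction is 0.536 instead of 0.5. The 50% versus 30% ratio becomes (0.5 + 0.5 × 0.536)/(0.7 + 0.3 × 0.536) = 0.768/0.861 = 0.89. The change is small.

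*Earlier stopping.* If stoppers leave at about week 8 (fraction 0.15), 45% versus 35% gives (0.55 + 0.45 × 0.15)/(0.65 + 0.35 × 0.15) = 0.618/0.703 = 0.88. For 50% versus 30% the ratio is 0.575/0.745 = 0.77.

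*Percentages.* The chance of at least one episode is 1 − [(1 − w)e^(−rT) + w e^(−rT/2)], with T = 1.077. At an assumed r = 0.25 episodes per year, 50% versus 30% gives 18.1% versus 20.3%, a ratio of 0.89. The percentage is affected almost as much as the count.

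Under these assumptions the exposure-adjusted rate ratio is 1.00 in every row.

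**Can the AE denominator be reused as it stands?** Not quite. AE on-treatment time runs up to 14 days past the last dose, about 58 weeks for a completer. Diary reporting of hypoglycaemia stops at V25, about 56 weeks. Using 58 weeks under episodes collected over 56 would lower a completer's rate by about 1 − 56/58 = 3%. The AE on-treatment period also ends at the follow-up or last visit where that comes first, a limit absent from the treatment-emergent definition for hypoglycaemia.

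**The case against.** A reader might infer that 40% attrition makes the hypoglycaemia comparison distorted, or that it will hide an increase on liraglutide. The documents do not support either inference. The 40% is assumed, not observed, and has no split by arm. It also refers to withdrawal, which Protocol 6.5 and 8.1.10 separate from stopping trial product: a subject can stop the drug and remain in the trial. With the same stopping pattern in both arms the raw comparison is undistorted. Protocol 5.5 and 18.1 describe dose-dependent gastrointestinal events with early onset, and 6.5 makes intolerance a ground for stopping. That makes a difference between arms plausible, but settles neither its size nor its direction.

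Other points on that side also have force:

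- The summary is descriptive and no claim rests on it. This stands and limits the importance of the point.
- Exposure-years could be backed out from the AE tables by dividing event counts by rates. This is largely true, but it gives the AE denominator with the window mismatch shown above, and leaves the work to the reader.
- Serious episodes already enter the AE rate. True, but non-serious ones do not clearly do so.
- A rate per subject-year is not automatically unbiased. Dose escalation fills the first 4 to 8 weeks, with weekly visits at first and a glucose check at each visit. If episodes cluster there, the arm that stops sooner would show an inflated rate. This stands, and is why the rate should sit beside the counts and not replace them.

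**Conclusion.** The point holds in conditional form. The plan gives AEs a time base and gives hypoglycaemia none, although the treatment-emergent window depends on each subject's exposure and the stated aim is to compare arms. If on-treatment exposure differs between arms, counts and percentages would be distorted, in a direction that cannot be known in advance.

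For moderate differences around the plan's 40%, the distortion is about 6% to 12% under mid-treatment stopping, and larger if stopping is early. It is zero if the arms stop alike. These sizes rest on assumed splits, a constant and equal hazard, and withdrawal as a stand-in for stopping drug; none of them is a forecast. The matter is a worthwhile low-cost improvement, not a flaw that threatens a conclusion of the trial.

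**What to change.** In Protocol 17.4.1.2 and SAP 2.4.1.2, add treatment-emergent hypoglycaemic episodes per 1000 subject-years beside the counts and percentages, for each classification (ADA/ISPAD and Novo Nordisk/ISPAD).

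Define the denominator to match collection: from first dose to the earliest of 14 days after last dose, V25, or the last visit. Count in the rate only episodes within that window. Two details need stating:

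- Whether V25 means the scheduled week 56 visit or the end-of-treatment visit brought forward under Protocol 8.1.10 for subjects who stop early.
- That any in-trial rate must not use follow-up time after diary reporting has ended, since that would dilute it.

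Add a note that the rate assumes a roughly constant hazard and should be read with the counts, because episodes may cluster during dose escalation.

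The cost is one table column and one derived exposure variable. No new data are needed, and exposure time is already required for the AE rates.

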5.1 Type of trial

This is a 56-week double-blind, randomised, parallel-group, placebo-controlled, multi-national trial followed by a 26-week period off study-drug. The trial will be conducted in pubertal adolescents with obesity aged 12 to less than 18 years. Subjects will be randomised 1:1 to receive liraglutide or placebo. The randomisation will be stratified according to pubertal and glycaemic status (see Sections 5.2 and 11).

At least 30% of subjects will be from areas with lifestyle and nutrition comparable to those in the European Union. All subjects will undergo counselling in healthy nutrition and physical activity for weight loss and must be prescribed a structured programme from the beginning of the 12-week run-in period and continuing through the 26-week follow-up period off trial drug. The trial design is shown schematically below:

[figure not shown]

Figure 5-1 Trial design

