5.2 Rationale for trial design

This trial is designed in accordance with regulatory requirements³⁵ and guidelines^{34, 36}

The primary endpoint, change in BMI SDS, is selected based on EMA's recommendation for a primary endpoint in the assessment of efficacy of new medicinal products for the treatment of obesity in children³⁴. The primary endpoint is assessed at the end of the 56 week double blind period. Secondary endpoints are assessed at the end of 30, 56, and 82 weeks. The assessment of secondary endpoints at 30 weeks, including BMI SDS, is included as there is a likelihood of a high attrition rate in this population of adolescents. Efforts will be made to encourage retention.

First-line therapy in primary obesity should always be lifestyle modification, rather than pharmacotherapy. To reflect this, a 12-week run-in period has been included in the trial design. During the run-in period, a structured counselling programme in healthy nutrition and physical activity is implemented in alignment with CHMP guidelines³⁴.

The 56-week treatment period is designed to be double-blind in order to avoid/minimise bias during the assessment of the primary endpoint. Randomisation is another measure used to minimise bias and is expected to lead to comparable subject populations at baseline in the liraglutide and placebo groups. Stratification according to Tanner staging as described in Section 8.4.7 will be used to enable the examination of treatment effect consistency across trial population subgroups. Stratification will also be performed according to glycaemic status: normoglycaemia versus dysglycaemia (pre-diabetes and T2DM).

Table 5–1 Glycaemic category

Normoglycaemia	FPG <5.6 mmol/L (<100 mg/dL) and/or HbA _{1c} <5.7%
Pre-diabetes	FPG 5.6–6.9 mmol/L (both inclusive), FPG 100–125 mg/dL (both inclusive) or HbA _{1c} 5.7–6.4% (both inclusive)
Type 2 diabetes (T2DM)	FPG ≥7.0 mmol/L (≥126 mg/dL) and/or HbA _{1c} ≥6.5%

Adapted from³⁷

The stratification is controlled by interactive web response system (IWRS); see Section 11.

Dysglycaemia is expected to occur frequently in this trial population. No interaction was observed between glycaemic status and body weight in the adult trial (NN8022-1839: Effect of liraglutide on body weight in non-diabetic subjects with obesity or overweight subjects with co-morbidities), and a similar pattern of AEs was observed in sub-populations by pre-diabetes status at screening.

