- Documented symptomatic hypoglycaemia: An episode during which typical symptoms of hypoglycaemia are accompanied by a measured plasma glucose concentration ≤ 3.9 mmol/L (70 mg/dL).
- Pseudo-hypoglycaemia: An episode during which the person with diabetes reports any of the typical symptoms of hypoglycaemia with a measured plasma glucose concentration > 3.9 mmol/L (70 mg/dL) but approaching that level.
- Probable symptomatic hypoglycaemia: An episode during which symptoms of hypoglycaemia are not accompanied by a plasma glucose determination but that was presumably caused by a plasma glucose concentration ≤ 3.9 mmol/L (70 mg/dL).

Note: Glucose measurements are performed with capillary blood calibrated to plasma equivalent glucose values

PG: plasma glucose SMPG: Self-measured plasma glucose

Figure 17–2 ADA/ISPAD classification of hypoglycaemia in paediatrics

Anti-liraglutide antibodies

Anti-liraglutide antibodies will be summarised in terms of the number and percentage of subjects per visit that are antibody-positive, antibody-negative, cross-reacting and in vitro neutralising.

In addition, a comparison of the change in HbA_{1c} and body weight between antibody-positive and antibody-negative subjects will be performed using descriptive statistics and graphs. Listings with the individual antibody results will also contain information about the HbA_{1c} levels and body weight measurements. The impact of anti-liraglutide antibodies on safety will be similarly assessed by descriptive comparisons between antibody-positive and antibody-negative subjects.

Bone age assessment

Bone age assessment at baseline and change in bone age assessment will be summarised using descriptive statistics.

ECCG

Summary statistics and the frequencies of shifts from baseline at 30 and 56 weeks will be tabulated for each treatment group.

Pulse

Summary statistics and the frequencies of shifts from baseline to 30 and 56 weeks and from 56 weeks to 82 weeks will be tabulated for each treatment group. In addition, statistical analyses similar to those made for blood pressure will be performed for change from baseline to 30 and 56 weeks.

Laboratory parameters

Summary statistics will be tabulated for each laboratory parameter. The distributions will also be presented graphically using box plots by treatment and week.

For each laboratory parameter, the values will be compared to the relevant reference ranges. The results will be presented as follows:

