2.2 Cut off points for diet maintenance

Table 2 International cut off points for BMI for obesity by sex for children between 12 and 17 years old, defined to pass through BMI of 25 kg/m² at age 18. Obtained by averaging data from Brazil, Great Britain, Hong Kong, Netherlands, Singapore, and United States.

Age: Years	BMI 30 kg/m ²	
	Males	Females
12	21.22	21.68
12.5	21.56	22.14
13	21.91	22.58
13.5	22.27	22.98
14	22.62	23.34
14.5	22.96	23.66
15	23.29	23.94
15.5	23.60	24.17
16	23.90	24.37
16.5	24.19	24.54
17	24.46	24.70
17.5	24.73	24.85
18	25	25

Adapted from Cole et al.¹

3 Determination of a subject's BMI > 95th percentile

In order to determine whether a subject is eligible according to inclusion criterion no.3, the investigator should use Table 2 for females and Table 3 for males. Based on the subject's age, it can be determined if the BMI is above the 95th percentile.

Table 3 BMI-for-age-FEMALES (12-18 years old)

Year: Month	Month	95th percentile (BMI in kg/m ²)
12:0	144	23.3
12:1	145	23.4
12:2	146	23.5
12:3	147	23.6
12:4	148	23.7
12:5	149	23.8
12:6	150	23.9
12:7	151	23.9
12:8	152	24.0
12:9	153	24.1
12:10	154	24.2
12:11	155	24.3

Year: Month	Month	95th percentile (BMI in kg/m²)
13:0	156	24.4
13:1	157	24.5
13:2	158	24.6
13:3	159	24.7
13:4	160	24.8
13:5	161	24.9
13:6	162	25.0
13:7	163	25.1
13:8	164	25.1
13:9	165	25.2
13:10	166	25.3
13:11	167	25.4
14:0	168	25.5
14:1	169	25.6
14:2	170	25.6
14:3	171	25.7

Year: Month	Month	95th percentile (BMI in kg/m²)
14:4	172	25.8
14:5	173	25.9
14:6	174	25.9
14:7	175	26.0
14:8	176	26.1
14:9	177	26.1
14:10	178	26.2
14:11	179	26.3
15:0	180	26.3
15:1	181	26.4
15:2	182	26.5
15:3	183	26.5
15:4	184	26.6
15:5	185	26.6
15:6	186	26.7
15:7	187	26.7

Year: Month	Month	95th percentile (BMI in kg/m²)
15:8	188	26.8
15:9	189	26.8
15:10	190	26.9
15:11	191	26.9
16:0	192	27.0
16:1	193	27.0
16:2	194	27.1
16:3	195	27.1
16:4	196	27.1
16:5	197	27.2
16:6	198	27.2
16:7	199	27.2
16:8	200	27.3
16:9	201	27.3
16:10	202	27.3
16:11	203	27.4

Year: Month	Month	95th percentile (BMI in kg/m²)
17:0	204	27.4
17:1	205	27.4
17:2	206	27.4
17:3	207	27.5
17:4	208	27.5
17:5	209	27.5
17:6	210	27.5
17:7	211	27.6
17:8	212	27.6
17:9	213	27.6
17:10	214	27.6
17:11	215	27.6
18	216	27.7

Table 4 BMI-for-age-MALES (12-18 years old)

Year: Month	Month	95th percentile (BMI in kg/m²)
12:0	144	22.1
12:1	145	22.2
12:2	146	22.3
12:3	147	22.3
12:4	148	22.4
12:5	149	22.5
12:6	150	22.6
12:7	151	22.7
12:8	152	22.8
12:9	153	22.9
12:10	154	23.0
12:11	155	23.1
13:0	156	23.1

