2.4.1.2 Safety endpoints

Descriptive statistics for all safety endpoints mentioned below will be provided with the aim to compare liraglutide 3.0 mg and placebo. All analyses and tabulations will be done using the safety analysis set. Unless otherwise stated, no formal statistical analyses are planned for the safety endpoints.

- Number of treatment emergent adverse events
- Number of treatment emergent hypoglycaemic episodes:
 - According to ADA/ISPAD classification
 - According to Novo Nordisk/ISPAD classification
- Occurrence of anti-liraglutide antibodies
- Change from baseline to 56 weeks in bone age assessment
- Change from baseline to 30 and 56 weeks in:
 - Pulse
 - Electrocardiogram (ECG)
 - Laboratory parameters:
 - Haematology: haemoglobin, haematocrit, thrombocytes, erythrocytes, leucocytes, differential count (eosinophils, neutrophils, basophils, lymphocytes, monocytes)
 - Biochemistry: creatinine, creatinine kinase, urea (BUN), albumin, bilirubin (total), alanine aminotransferase (ALT), aspartate aminotransferase (AST), alkaline phosphatase (ALP), sodium, potassium, calcium total, calcium, albumin-corrected, amylase, lipase, and carcinoembryonic antigen (CEA)
 - Hormone levels: calcitonin, insulin-like growth factor-1 (IGF-1), thyroid stimulating hormone (TSH), free thyroxine (free T4), dehydroepiandrosterone sulfate (DHEAS), luteinising hormone (LH), follicle stimulating hormone (FSH), estradiol (females), testosterone (males), prolactin, adrenocorticotrophic hormone (ACTH), cortisol
 - Bone metabolism markers: Type 1 collagen N-telopeptide (NTX1), type 1 C-telopeptide (CTX1), procollagen 1 N-terminal propeptide (P1NP), alkaline phosphatase (bone)
 - Pubertal status
 - Physical examination
 - Height standard deviation score (SDS)
 - Mental health assessed by Columbia Suicidality Severity Rating Scale (C-SSRS) and Patient Reported Health Questionnaire 9 (PHQ-9)

- Change from 56 weeks to 82 weeks in:
 - Pulse
 - Laboratory parameters:
 - Haematology: haemoglobin, haematocrit, thrombocytes, erythrocytes, leucocytes, differential count (eosinophils, neutrophils, basophils, lymphocytes, monocytes)
 - Biochemistry: creatinine, creatinine kinase, urea (BUN), albumin, bilirubin (total), alanine aminotransferase (ALT), aspartate aminotransferase (AST), alkaline phosphatase (ALP), sodium, potassium, calcium total, calcium, albumin- corrected, amylase, lipase, and carcinoembryonic antigen (CEA)

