3.2 Supportive secondary efficacy endpoints

- All the secondary supportive analysis will be performed on in-trial period.
- To analyse the change in BMI SDS from week 56 to week 82 subjects who have completed the treatment (treatment completers), only their assessment at week 56 will be considered as baseline. No change from week 56 to 82 will be calculated for treatment discontinued subjects and for withdrawn subjects unless they have week 56 visit assessment collected.
- Multiple imputation will not to be considered for change in BMI SDS from week 56 to 82 parameter if there is no missing assessment.
- Tanner stage and glycaemic category collected at randomisation visit will be considered as fixed effect while performing ANCOVA for change from baseline to week 30, 56 and 82 and change from week 56 to 82.
- For “percentage of subjects achieving $\geq 5\%$ reduction” and “Percentage of subjects achieving $\geq 10\%$ reduction” in baseline BMI at week 30, 56 and 82. Missing imputation will be handled as mentioned in section [2.3](#) with the baseline BMI as covariate instead of baseline BMI SDS.
- Body weight with standard units (Kg) will only be used in all summary and analysis outputs.

Below additional supportive secondary endpoint is been included in section [2.4](#)

- Change from baseline to 30 and 56 weeks in:
 - BMI SDS (%)

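### The antibody comparison uses body weight as its only weight-related measure in growing adolescents; add change in BMI SDS and show age, sex and Tanner stage by antibody group

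*Protocol*

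**What the plan says.** Protocol 17.4.1.2, under anti-liraglutide antibodies, says that a comparison of change in HbA1c and "body weight between antibody-positive and antibody-negative subjects will be performed using descriptive statistics and graphs". The same paragraph continues: "Listings with the individual antibody results will also contain information about the" HbA1c levels and body weights. BMI SDS is not mentioned, and no adjustment or stratification by age, sex, Tanner stage or height is named.

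Protocol 8.5.5 restricts antibody analysis to samples from liraglutide-treated subjects. On the population, Protocol 5.1 says: "The trial will be conducted in pubertal adolescents with obesity aged 12 to less than 18 years".

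The SAP leaves this as it is. Section 2.4.1.2 lists antibody occurrence among the safety endpoints and says that, unless otherwise stated, "no formal statistical analyses are planned for the safety endpoints". Section 2.7 summarises endpoints by treatment group, not by antibody status. The changes to the safety analyses in section 3.3 do not mention antibodies.

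BMI SDS is the primary endpoint at week 56 and a supportive endpoint at week 30. SAP 2.5.1 derives it from the WHO reference at the subject's age. SAP Table 3-2 shows height visits at weeks 0, 30 and 56.

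**The concern.** A 12-year-old and a 17-year-old who both hold their relative position gain different amounts of weight in 56 weeks. Between randomised arms this tends to balance, and the body-weight ANCOVA in Protocol 17.4.1.1 also adjusts for age, sex and Tanner stratum. Antibody-positive and antibody-negative subjects are not randomised groups, yet their comparison has no such protection. Placebo subjects have no antibody result, so they offer no growth reference by antibody status.

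This is the plan's only stated look at whether antibodies go with a smaller weight effect. A younger antibody-positive group could appear to respond less well, and an older one could appear to respond better, for reasons of growth.

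**Working it through.** **Size of the groups.** The plan gives no figure for the antibody comparison, so its sample size serves only to fix the liraglutide arm. The inputs from Protocol 17.1 are a difference of -0.26, SD 0.35 and 40% withdrawal.
- Diluted difference: 0.6 x 0.26 = 0.156.
- Liraglutide-arm variance: 0.35² + 0.4 x 0.6 x 0.26² = 0.1387. Placebo-arm variance: 0.1225.
- Pooled SD: √[(0.1387 + 0.1225)/2] = 0.361.
- A two-sided 5% t-test at 90% power then needs 228 in total, as stated (226 by the normal approximation). Half of 228 is 114 on liraglutide.

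**Growth at constant height.** Appendix A Tables 3 and 4 give the BMI on the 95th percentile. Height is ASSUMED to be 1.60 m throughout (1.60² = 2.56). Expected gain over 56 weeks = BMI increment x 2.56 x 56/52.

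| | BMI from age 12 to 13 | Gain | BMI from age 17 to 18 | Gain | Per year of age |
|---|---|---|---|---|---|
| Girls | 23.3 to 24.4 (+1.1) | 3.0 kg | 27.4 to 27.7 (+0.3) | 0.8 kg | (3.0 - 0.8)/5 = 0.4 kg |
| Boys | 22.1 to 23.1 (+1.0) | 2.8 kg | 26.9 to 27.5 (+0.6) | 1.7 kg | (2.8 - 1.7)/5 = 0.2 kg |

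**Adding height growth.** ASSUME that the 12-year-old girl grows 5 cm at BMI 30 and the 17-year-old does not grow. The extra gain is 30 x (1.65² - 1.60²) = 4.9 kg, and the gradient becomes (3.0 + 4.9 - 0.8)/5 = 1.4 kg per year of age. This sets the range of roughly 0.2 to 1.4 kg.

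**Second calculation.** This uses the obesity line in Appendix A Table 1 with different ASSUMED heights: 1.50 m at age 12, and at age 17 1.75 m (boys) or 1.65 m (girls). Gain = BMI₁ x height₁² - BMI₀ x height₀².
- With growth of 4 cm at 12 and 0.5 cm at 17, boys gain 5.3 and 2.5 kg, and girls 6.0 and 1.4 kg. The gradients are (5.3 - 2.5)/5 = 0.6 and (6.0 - 1.4)/5 = 0.9 kg per year of age.
- With growth of 2 to 8 cm at 12 and 0 to 2 cm at 17, the extremes are (3.6 - 4.1)/5 = -0.1 kg (boys) and (9.5 - 0.9)/5 = 1.7 kg (girls).

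**How large an age gap chance could give.** ASSUME that 5% to 20% of the 114 are antibody-positive (6 to 23 subjects) and that the SD of age is 1.5 to 1.73 years. SE of the gap in mean age = SD x √(1/n₊ + 1/n₋).
- 6 against 108: 0.63 to 0.73 years. One year is 1.59 to 1.38 SE, a two-sided chance of about 11% to 17%.
- 23 against 91: 0.35 to 0.40 years. One year is 2.86 to 2.48 SE, a chance of about 0.4% to 1.3%.

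**On the BMI SDS scale.** SAP 2.5.1 evaluates its reference values at the subject's age. A subject who keeps the same SDS therefore shows no change, however much weight growth has added.

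**The case against.** The strongest objection is that the drift is small beside sampling error. As a scale check, take the SD of 0.35 and the 5.58 kg/m² per SDS unit from the SAP's worked example of an 11-year-old boy (illustrative only). At 1.60 m the SD of weight change is 0.35 x 5.58 x 2.56 = 5.0 kg. The SE of the comparison is then about 1.2 kg (23 against 91) to 2.1 kg (6 against 108). One SE of age gap at 1.4 kg per year shifts it by at most 0.40 x 1.4 = 0.6 kg or 0.73 x 1.4 = 1.0 kg, under half the noise in each case. This stands: growth is one source of error among larger ones. It does not argue against showing a measure that is already derived.

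Several stronger readings are tempting and are not supported:
- **Growth will mimic or hide a loss of effect.** It shifts the result only if the groups differ in age, sex or puberty, and the documents do not say that they will.
- **BMI SDS was made primary because weight depends on age.** Protocol 5.2 gives another reason: "The primary endpoint, change in BMI SDS, is selected based on" the EMA's recommendation.
- **HbA1c is uninformative because most subjects are normoglycaemic.** No proportion is given, and Protocol 5.2 expects dysglycaemia to be frequent. HbA1c is a legitimate part of the comparison; it simply does not measure the weight effect.
- **The comparison is fixed in raw kilograms.** Protocol 17.4.1.2 names no unit. SAP 3.2 says "Body weight with standard units (Kg) will only be used in all summary and analysis outputs", which may only drop pounds, since SAP Table 2-4 analyses both kg and percent. Percent change would still carry growth.
- **BMI SDS removes the problem by construction.** The drift is zero only at constant SDS. The conversion depends on age and sex, so the same BMI loss gives different SDS changes, and the primary model itself keeps age, sex and Tanner stratum.

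**Conclusion.** The point holds as a minor improvement. The only weight-related measure in the antibody comparison carries growth, and neither document adjusts for it. The possible shift is roughly 0.2 to 1.4 kg per year of difference in mean age, or about -0.1 to 1.7 kg under wider assumptions. All these figures rest on assumed heights. A gap near one year is plausible mainly with few positives, and that rests on an assumed prevalence and age SD.

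A reader might infer that the plan would reach a wrong conclusion about antibodies. The documents do not support that: the display is descriptive, with no test, threshold or decision rule. The primary analysis, the sample size and the significance level are untouched.

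**What to change.** Amend the antibody paragraph of Protocol 17.4.1.2, or record the change in SAP 3.3, along these lines:

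*Among liraglutide-treated subjects, change from baseline to weeks 30 and 56 in BMI SDS, body weight and HbA1c will be summarised and plotted by antibody status. Baseline age, sex and Tanner stage will be tabulated for the same groups. The individual antibody listings will also show BMI SDS.*

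The baseline table matters because BMI SDS removes most, but not all, of the dependence on age and sex; it lets the reader see whether an imbalance exists. The cost is one more variable in planned outputs and one small table. No new data or visits are needed, and the comparison stays descriptive.
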